10.0 STATISTICAL CONSIDERATIONS

Data analysis plan: We will use descriptive statistics to characterize the feasibility and process measures listed in Table 5, with 95% confidence intervals. Changes in UFS-QOL scores, the primary outcome, as well as secondary outcomes including hormone levels and fibroid volume, will be compared using linear mixed models for repeated measures, adjusting for baseline. We will estimate 1) between-group differences in change from baseline to months 1 and 2; 2) changes from baseline to months 1-3 and 4-6 in group A; and 3) changes from month 3 to months 5 and 6 within group B.

Sample size calculations: This is a pilot study with the aim of assessing the feasibility of implementing a definitive letrozole trial. Therefore, we chose a sample size that would be large enough to assess feasibility, but small enough to complete the pilot within a the1 year timeframe and with a limited budget. Accordingly, the study will not have power to detect small treatment effects. In the PROMISe pilot study discussed in Preliminary Studies, the standard deviation of the UFS-QOL SSS was 20, and correlation of baseline with follow-up scores declined from 0.5 at 1 month to nearly zero at 3 months. In the analysis for AIM 2 of between-group differences in the change in UFS-QOL from baseline to 2 months , the sample size of 20 will provide 80% power to detect a between-group difference of 13.4 points in average SSS scores at months 1 and 2, after accounting for short term attrition of 10%. In the analysis for AIM 3, assessing longer term changes in SSS scores within group A, the sample of 15 women have 80% power to detect average changes from baseline to months 1-3 and 4-6 of 16.0 points. In additional analysis for AIM 3, assessing changes from month 3 to months 5-6 in group B, the corresponding minimum detectable effect will be 18 points. Effects of this magnitude are

clinically relevant because 15-20 points is the mean difference in SSS between women with symptomatic fibroids and women without fibroids.

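### One 16.0-point detectable change is printed for both Group A windows; on the plan's own SD and correlations it fits months 1-3 but is too small for months 4-6

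*Combined protocol and SAP*

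**What the plan says.** All of this is in section 10.0, Statistical Considerations.

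- Variability of the symptom score, from an earlier pilot: "the standard deviation of the UFS-QOL SSS was 20".
- Correlation, from the same source: "correlation of baseline with follow-up scores declined from 0.5 at 1 month to nearly zero at 3 months".
- The planned Group A estimates, listed as two windows: "changes from baseline to months 1-3 and 4-6 in group A".
- The power statement, which gives both windows one figure: "80% power to detect average changes from baseline to months 1-3 and 4-6 of 16.0 points". The sample is given in the same sentence: "assessing longer term changes in SSS scores within group A, the sample of 15 women have 80% power".
- The Group B counterpart: "assessing changes from month 3 to months 5-6 in group B, the corresponding minimum detectable effect will be 18 points".
- The model: "linear mixed models for repeated measures, adjusting for baseline".

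The section then calls effects of this size clinically relevant, by comparison with a 15-20 point mean difference between women with symptomatic fibroids and women without fibroids. For these power figures it does not state alpha, sidedness, the correlation at 2 months, the correlation among follow-up scores or the standard-error formula. Section 3.0 randomizes 20 women 1:1, so Group A has 10.

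**The concern.** The SD of a change from baseline depends on how strongly follow-up correlates with baseline. By the plan's account that correlation is material early in months 1-3 and about zero throughout months 4-6. The two changes therefore have different SDs, and one number cannot be the 80%-power detectable change for both.

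The affected window matters. Section 4.0 gives Group A the task of informing letrozole use beyond 3 months, and months 4-6 are that period. If readers credit the late window with 80% power at 16.0 points, they may take an inconclusive late result as evidence that the symptom effect has faded. The pilot is meant to guide the dosing regimen of a larger trial.

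**Working it through.** **Inputs from section 10.0:** SD 20; correlation with baseline 0.5 at 1 month and about 0 at 3 months; 15 women; 80% power; 16.0 points.

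**Assumed, because the plan does not say:** two-sided 5%; a one-sample test of (window mean minus baseline); correlation depending only on time lag. Three lag patterns were tried: 0.5/0.25/0 at 1, 2 and 3 or more months; AR(1) with 0.5; and 0.5/0/0.

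**Formulas**

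- SD of change = 20 × √(1 + v − 2r), where v is the variance factor of the three-month mean and r is the average correlation of those months with baseline.
- Detectable change, normal approximation (z) = (1.960 + 0.842) × SD/√n, which is 0.723 × SD at n = 15.
- Detectable change, exact t = 0.778 × SD at n = 15 and 0.996 × SD at n = 10.

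**Worked case, pattern 0.5/0.25/0**

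- v = (3 + 2 × (0.5 + 0.5 + 0.25))/9 = 0.611 for either window.
- Months 1-3: r = (0.5 + 0.25 + 0)/3 = 0.25. SD = 20 × √(1.611 − 0.5) = 21.1.
- Months 4-6: r = 0. SD = 20 × √1.611 = 25.4.

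**Step 1: reproduce 16.0 (months 1-3, n = 15)**

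| Pattern | SD | Detectable, z | Detectable, t | Power at 16.0, z / t |
|---|---|---|---|---|
| 0.5/0.25/0 | 21.1 | 15.2 | 16.4 | 84% / 78% |
| AR(1) 0.5 | 20.3 | 14.7 | 15.8 | 86% / 81% |
| 0.5/0/0 | 22.1 | 16.0 | 17.2 | 80% / 74% |

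The printed figure fits this window.

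**Step 2: same method, months 4-6, n = 15**

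| Pattern | SD | Detectable, z | Detectable, t | Power at 16.0, z / t |
|---|---|---|---|---|
| 0.5/0.25/0 | 25.4 | 18.4 | 19.8 | 69% / 62% |
| AR(1) 0.5 | 24.8 | 17.9 | 19.3 | 71% / 64% |
| 0.5/0/0 | 24.9 | 18.0 | 19.4 | 70% / 64% |

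**Step 3: relax the follow-up correlation.** Hold the late correlation with baseline at zero and give months 4, 5 and 6 any common correlation from 0 to 1. Power at 16.0 then runs from 59% to 77% (z) or 53% to 70% (t). The detectable change runs from 16.7 to 20.5 (z) or 18.0 to 22.0 (t).

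**Step 4: what would rescue 16.0 in months 4-6?** With v = 0.611, r would have to be about 0.19 (z) or 0.28 (t). If months 4-6 were mutually independent, r = 0.055 (z) would be enough. But independent follow-up months sit badly with a correlation of 0.5 at a one-month lag. With v = 1/3 and r = 0.25, the months 1-3 figure would also fall to 0.723 × 20 × √(1.333 − 0.5) = 13.2. The two windows would still need different figures.

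**Step 5: the arm as randomized (n = 10, before attrition)**

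- Months 1-3: 18.0-19.6 (z), 20.2-22.0 (t).
- Months 4-6: 22.0-22.5 (z), 24.7-25.3 (t). Power at 16.0 points is about 43-53%.

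**The case against.** **Unstated inputs.** The plan does not give alpha, sidedness or the standard-error formula, and it names baseline-adjusted mixed models, not raw change scores. Other readings do return about 16.0 for months 4-6:

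- One-sided 5% with z gives 15.9-16.3. The same rule gives 13.0-14.2 for months 1-3, and 15.1-17.0 for Group B against the printed 18.
- A baseline-adjusted residual SD of about 15.6, with the 15 women taken as both groups together (7.5 each), gives 16.0 by z. This contradicts the wording that places the 15 in Group A, treats the baseline mean as known, and has only 66% power by t. Months 1-3 would then be 15.15 or less, so 16.0 would be conservative there.
- One average over months 1-6 gives 16.0 (AR(1), t, n = 15), but the analysis plan lists two windows.

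None of these fits the wording and the other printed figures together, but they do make the power loss conditional. Nearly zero is also not a number: with v = 0.611, a residual correlation of 0.15 would give 77% power by z.

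**Stronger readings a reader might infer.** Three are not supported:

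- That the paragraph contradicts itself because months 4-6 gets 16.0 while Group B gets 18. With correlations of 0.5 at 1 month and 0 at 3 months, and c at 2 months, the variance factors are 1.556 + 0.222c for months 4-6 and 1.75 − c for Group B. They cross at c = 0.16. The plan does not give c, and at c = 0 Group B is the more variable (SD 26.5 against 24.9).
- That the early-window SD was carried over to the late window. The numbers are compatible with this, but the calculation is not documented.
- That the clinical-relevance sentence fails on this ground alone. At 15 women, the 18-20 points for months 4-6 still lie within 15-20.

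**Weight.** It is fair to say that this is a feasibility pilot, that no decision rule uses 16.0, and that printing 15 women for an arm of 10 is the larger error. Correcting n with one common SD would still leave the months 4-6 figure too small.

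**Conclusion.** The point holds in a limited form. On the plan's SD, correlations and 15 women, and assuming a two-sided 5% test of change from baseline, 16.0 points is a sound detectable change for months 1-3 (about 15-17) but not for months 4-6 (about 18-20). Late-window power at 16.0 is about 62-71% under the three lag patterns. It is 53-77% over any common follow-up correlation from 0 to 1 with zero correlation to baseline. All of these are below the stated 80%.

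The exact shortfall rests on inputs that the plan omits. The need for separate figures is firmer: none of the readings examined that keep the two windows apart gives both the same detectable change. This is a misstated power figure in a pilot. It does not threaten the design.

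**What to change.** In section 10.0, replace the single Group A figure with one detectable change for baseline to months 1-3 and one for baseline to months 4-6, each from its own change SD. State the alpha, sidedness, correlations (including 2 months and among follow-up scores), standard-error formula and number of women used.

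Compute both at the Group A size that 1:1 allocation of 20 provides, less expected attrition. At 10 women, under the assumptions above, expect about 18-22 points for months 1-3 and 22-25 for months 4-6. The plan gives only a 10% short-term attrition rate, so it should also state the rate assumed through month 6.

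Limit the clinical-relevance sentence to contrasts whose restated figure lies within 15-20 points. At 10 women, months 4-6 would fall outside it.

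The cost is one recalculation and a few sentences, with no extra patients or procedures. The downside is less favourable stated detectable effects.
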